MCV	mean corpuscular volume
MI	Multiple Imputations
NA	not applicable
[REDACTED]	[REDACTED]
OL-LTE	Open-Label, Long-Term Extension study
P/C	phone contact
PGA	Physician's Global Assessment
PK	Pharmacokinetic(s)
[REDACTED]	[REDACTED]
PP	per protocol
PP-NRS	Peak Pruritus-Numeric Rating Scale
QD	once daily
RBC	red blood cell(s)
SAE	serious adverse event
SD	standard deviation
[REDACTED]	[REDACTED]
TEAE	treatment emergent adverse event
TF	Treatment Failure
ULN	upper limit of normal
US	United States
V	visit
vIGA-AD™	validated Investigator Global Assessment for Atopic Dermatitis
WBC	white blood cell(s)
WOCBP	women of child-bearing potential
[REDACTED]	[REDACTED]

Synopsis

Name of Sponsor/Company:					
Dermavant Sciences, Inc.					
Name of Investigational Product:					
DMVT-505 (tapinarof cream, 1%)					
Name of Active Ingredient:					
Tapinarof					
Protocol Number:	DMVT-505-3101	Phase:	3	Country:	United States (US) and Canada
Title of Study:					
A Phase 3 Efficacy and Safety Study of Tapinarof for the Treatment of Moderate to Severe Atopic Dermatitis in Children and Adults					
Study Sites(s):					
Up to approximately 60 sites in the US and Canada					
Objectives:					
Primary:					

To evaluate the efficacy of tapinarof cream, 1% once daily (QD) compared with vehicle control in subjects with atopic dermatitis (AD)					
Secondary:					

To further characterize the efficacy of tapinarof cream, 1% QD compared with vehicle control over timeTo evaluate the safety and tolerability of tapinarof cream, 1% QD in subjects with ADTo describe the effect of tapinarof cream, 1% QD on AD symptom severity and the associated impact on daily activities and attitudes in subjects with ADTo evaluate plasma concentrations of tapinarof in subjects with AD					
Methodology:					
This is a double-blind, randomized, vehicle-controlled, Phase 3, multicenter study to evaluate the efficacy and safety of topical tapinarof cream, 1% compared with vehicle control cream in subjects ages 2 years and above with AD.					
Following a 30-day screening period, eligible subjects will be randomized at a 2:1 ratio to receive QD treatment with tapinarof cream, 1% or vehicle cream. Subjects will return to the clinic at Weeks 1, 2, 4, and 8 for efficacy and safety assessments. Subjects will be contacted by phone at Weeks 3 and 6 to assess AEs and concomitant medications, to review study drug administration instructions, and to confirm subject's continued participation in this study.					
Study drug will be dispensed and applied during the clinic visits and will be administered at home between clinic visits as instructed by site personnel. Subjects or their caregivers will be instructed to apply study drug QD to all affected areas, including newly appearing lesions and lesions/areas that improve during the study. Subjects or caregivers will apply sufficient study drug to cover completely each lesion with a thin layer of study drug and will record the time of study drug application and daily itch score (Peak Pruritus-Numeric Rating Scale [PP-NRS]) in a daily diary provided by the study site. (Note that subjects are allowed, but not required, to treat scalp lesions with study drug; however, efficacy analyses will not include assessment of AD in this area.) Subjects or caregivers will be advised to maintain the approximate dosing time chosen at the beginning of the study for their full study participation. At the phone contacts at Weeks 3 and 6, subjects should be reminded to complete their daily diary and bring it with them to the next clinic visit.					
Study drug application instructions will be reviewed at all post-randomization clinic visits and during any planned study phone calls. On clinic visit days, subjects will be instructed/reminded how to apply study drug (except during the final treatment/end-of-study visits). During the clinic visits, subjects or caregivers will apply the daily dose of study drug while on-site under the supervision of site personnel. The time of the dose application and assessments will depend on the time of the clinic visit. Therefore, the timing of the clinic visit may lead to a change in the subject's chosen dosing time for that day.					
At the end of the 8 weeks of treatment in this study, subjects will have the option to enroll in an Open-Label, Long-Term Extension (OL-LTE) study for an additional 48 weeks of treatment. Subjects who choose not to participate in the OL-LTE study or who fail to qualify for participation in the OL-LTE study will complete a Follow-up Visit (Week 9 visit) approximately 1 week after the end of treatment in this study. Subjects who withdraw from the study before Week 8 will complete an Early Termination Visit and are not eligible for the OL-LTE study.					

Number of Subjects:

Approximately 400 subjects ages 2 years and above will be enrolled in the study, randomized at a 2:1 ratio to receive tapinarof cream, 1% (approximately 267 subjects) or vehicle cream (approximately 133 subjects). Subjects will be stratified so that a minimum of 10% will have severe disease (validated Investigator Global Assessment in Atopic Dermatitis [vIGA-ADTM] = 4) and the remainder will have moderate disease (vIGA ADTM = 3). A minimum of approximately 15% of subjects will be enrolled into each of the following age groups: 2-6 years, 7-11 years, 12-17 years, 18 years and above. Adults 18 years and above will comprise a maximum of 20% of enrolled subjects.

Diagnosis and Main Criteria for Inclusion:

Inclusion Criteria:

Each subject must meet all the following criteria to be eligible to participate in the study:

1. Male and female subjects ages 2 years and above with clinical diagnosis of AD by Hanifin and Rajka criteria.
2. Subjects with AD covering $\geq 5\%$ and $\leq 35\%$ of the body surface area (BSA). Scalp should be excluded from the BSA calculation to determine eligibility during Screening and at Baseline, and for all efficacy assessments.
NOTE: Subjects with disease only on palms and soles are not eligible.
3. A vIGA-ADTM score of ≥ 3 at Screening and Baseline (pre-randomization).
4. An Eczema Area and Severity Index (EASI) score of ≥ 6 at Screening and Baseline (pre-randomization).
5. AD present for at least 6 months for ages 6 years old and above or 3 months for ages 2 to 5 years old, confirmed by prior medical documentation and/or according to the subject/caregiver report.
6. Female subjects of childbearing potential who are engaging in sexual activity that could lead to pregnancy should use one of the following acceptable birth control methods while on study and for 4 weeks after the last exposure to study drug.
 - Acceptable contraception methods include intrauterine device, hormonal contraceptives, barrier method (e.g., condom or diaphragm), or surgical sterilization of male partner (vasectomy)
 - Subjects who claim abstinence as their method of contraception are allowed provided they agree to use a barrier method (e.g., condom or diaphragm) should they become sexually active from Screening to 4 weeks after the last dose of study drug

Non-child-bearing potential is defined as:

- premenarchal
- pre-menopausal females with a documented bilateral tubal ligation, bilateral oophorectomy, hysterectomy, or hysteroscopic sterilization
- postmenopausal female with a cessation of menses for at least 12 months without an alternative medical cause; a blood sample with follicle stimulating hormone > 40 mIU/mL is confirmatory in questionable cases

7. Female subjects of childbearing potential must have a negative serum pregnancy test at Screening and a negative urine pregnancy test at Baseline (Day 1).
8. Subject, subject's parent(s), or legal representative must be capable of giving written informed consent/assent, which includes compliance with the requirements and restrictions listed in the consent/assent form; written informed consent must be obtained prior to any study related procedures.

Exclusion Criteria:

A subject who meets any of the following criteria will be excluded and considered ineligible for participation in the study:

1. Concurrent conditions:
 - a. Immunocompromised (e.g., lymphoma, acquired immunodeficiency syndrome) or history or evidence of active or latent tuberculosis or human immunodeficiency virus antibody as documented by medical history and/or according to the subject/caregiver report..
 - b. Chronic or acute systemic infection requiring treatment with antiparasitics or antiprotozoals, within 4 weeks prior to the Baseline visit.
 - c. Chronic or acute systemic bacterial infection requiring treatment with systemic antibiotics within one week prior to the Baseline visit.

- d. Chronic or acute superficial fungal infection requiring treatment with systemic antifungals within one week prior to the Baseline visit.
- e. Acute active bacterial, fungal, or viral (herpes simplex, herpes zoster, chicken pox) skin infection within 1 week prior to the Baseline visit; the condition should be completely resolved one week prior to Baseline Visit.
- f. Significant dermatologic or inflammatory condition other than AD that, in the Investigator's opinion, would make it difficult to interpret data or assessments during the study. For example, subjects with an active skin condition such as Kaposi's varicelliform eruption, scabies, molluscum contagiosum, impetigo, psoriasis, severe acne, connective tissue disorder, or Netherton's syndrome, or any other concurrent active disease.
- g. Concurrent skin lesions in the treatment area or pruritus due to conditions other than AD that, in the opinion of the Investigator, would either interfere with study evaluations or affect the safety of the subject.

2. Screening alanine aminotransferase (ALT) or aspartate aminotransferase (AST) $\geq 2.0 \times$ the upper limit of normal (ULN).
3. Screening total bilirubin $> 1.5 \times$ ULN; total bilirubin $> 1.5 \times$ ULN is acceptable if bilirubin is fractionated and direct bilirubin $< 35\%$.
4. Current or chronic history of liver disease, known hepatic or biliary abnormalities (with the exception of Gilbert's syndrome or asymptomatic gallstones), presence of hepatitis B surface antigen (HBsAg), or positive hepatitis C antibody test result, or presence of anti-hepatitis B core antigen (anti-HBc). Subjects having a negative HBsAg and a positive anti-HBc may enroll if they have a positive anti-hepatitis B surface antigen demonstrating natural immunity. Subjects with a history of hepatitis C virus infection who were medically cured and have an undetectable viral load are eligible to enroll. Subjects with a history of stable non-alcoholic fatty liver disease without evidence of active inflammation (elevated ALT/AST $\geq 2.0 \times$ ULN) or cirrhosis are eligible to enroll.
5. Current or a history of cancer within 5 years except for adequately treated skin basal cell carcinoma, cutaneous squamous cell carcinoma or carcinoma in situ of the cervix (surgical excision or electrodessication and curettage).
6. Subjects who would not be considered suitable for topical therapy (e.g., those with extensive disease involvement over a large BSA who would be candidates for systemic therapy).
7. Use of any prohibited medication or procedure within the indicated period before the Baseline visit.

NOTE: Prohibited concomitant medications, therapy, etc. during the defined period are as listed in the bullets below. If a subject requires any of these medications throughout the study period, he/she may be excluded from or discontinued from the study, at the discretion of the Investigator and Medical Monitor.

- a. From 4 months prior to Baseline until the completion of the Follow-up visit or study discontinuation:
 - DUPIXENT® (dupilumab) injection.
 - Any monoclonal antibody product that becomes approved for AD during the course of the trial.
- b. From 28 days prior to Baseline until the completion of the Follow-up visit or discontinuation:
 - Oral, injectable, and suppository preparations of corticosteroids. Eye drops and nasal preparations are allowed. Inhaled preparations are allowed when used for a stable condition and stable dose for ≥ 28 days before Screening and are continued at the same dose throughout the study.
 - Oral preparations and injections of immunosuppressants (cyclosporine, methotrexate, azathioprine, tacrolimus, Janus kinase inhibitors, etc.).
 - Excessive sun exposure, tanning booth, other ultraviolet light source and phototherapy including psoralen and ultraviolet A therapy or is unwilling to minimize natural and artificial sunlight exposure.
 - Treatment with antivirals with the exception of short-term treatment for acute upper respiratory viral infections (i.e., influenza) or viral suppressive therapy for a history of recurrent herpes labialis or genital herpes.
- c. From 14 days prior to Baseline until the completion of the Follow-up visit or discontinuation:
 - EUCRISA® (crisaborole) and any other PDE4 inhibitor.
 - Tacrolimus ointment and pimecrolimus cream.
 - Topical corticosteroids that are classified as medium or high potency (e.g., fluocinonide, triamcinolone acetonide) or super-high potency (e.g., clobetasol propionate). Eye drops and nasal preparations are allowed.

- Coal tar products (on the body). If subject chooses to treat scalp with study drug, then coal tar products are prohibited for use on the scalp.
- Over the counter or herbal medicines for AD (topical and oral preparations). If subjects are using emollients, they may continue to use the same emollient on nonlesional skin during the study. Emollients containing salicylic acid are prohibited during the study.

d. From 7 days prior to Baseline until the completion of the Follow-up visit or discontinuation:

- Topical corticosteroids that are classified as low potency (e.g., desonide, hydrocortisone).
- Oral, injectable, or intravenous antibiotics or antifungal medications.
- Topical doxepin, topical gentamicin, or topical neomycin sulfate.
NOTE: Oral doxepin is allowed for treatment of depression if subject has been on a stable dose (4 weeks) at Screening.
- Topical products containing urea, except for the treatment of follicular events.
- Antihistamines/antiallergics (oral, topical and injections): diphenhydramine, chlorpheniramine maleate, hydroxyzine.
NOTE: The following antihistamines are allowed from Screening throughout the treatment period: loratadine, fexofenadine hydrochloride, cetirizine hydrochloride. Subjects are allowed to switch from non-allowed antihistamines to allowed antihistamines during Screening but must be on a stable dose for 7 days prior to Baseline.

e. The subject has received an investigational product within the following time period prior to the first dosing day in the current study: Minimum of 30 days or 5 half-lives of the investigational product (whichever is longer).

8. A history of or ongoing serious illness or medical, physical, or psychiatric condition(s) that, in the Investigator's opinion, may interfere with the subject's participation in the study, interpretation of results, safety of the subject or ability to understand and give informed consent.

9. Pregnant females as determined by positive serum (Screening) or urine (Baseline) human chorionic gonadotropin test.

10. Lactating females.

11. History of sensitivity to the study medications, or components thereof or a history of drug or other allergy that, in the opinion of the Investigator or Medical Monitor, contraindicates their participation.

12. Previous known participation in a clinical study with tapinarof (previously known as GSK2894512 and WBI-1001).

Investigational Product, Dosage and Mode of Administration:

Tapinarof cream, 1% [REDACTED]
[REDACTED] is to be administered by the subject/caregiver QD via topical application of a thin layer to affected areas.

Reference Therapy, Dosage and Mode of Administration:

Vehicle cream [REDACTED] is to be administered by the subject/caregiver QD via topical application of a thin layer to affected areas.

Duration of Treatment:

- Subjects randomized to tapinarof cream, 1% will receive tapinarof for 8 weeks
- Subjects randomized to vehicle cream will receive vehicle for 8 weeks

The total study duration for subjects who complete this Phase 3 study and who fail to qualify for participation in the OL-LTE study, or who qualify to participate in the OL-LTE study but elect not to enroll in that study is up to 13 weeks in total (including up to 30 days screening, 8 weeks treatment, and a 1-week follow-up period).

Functional Outcomes and Quality of Life Analysis:

Change from Baseline in [REDACTED]

[REDACTED] Peak Pruritus-NRS scores will be analyzed using an ANCOVA model with treatment as a main effect, and baseline as a covariate.

Pharmacokinetic Analyses:

Plasma concentration data will be listed and summarized by study visit.

Schedule of Assessments

Table 1: Schedule of Assessments

Procedures and Assessment	Screening	Baseline	Double-Blind Vehicle-Controlled Treatment Phase						FU ^a	ET ^b
	V1	V2	V3	V4	P/C ^c	V5	P/C ^c	V6	V7	NA
	Day -30 to Day -1	Day 1	Week 1 Day 8 (±2 d)	Week 2 Day 15 (±2 d)	Week 3 Day 22 (±2 d)	Week 4 Day 29 (±2 d)	Week 6 Day 43 (±2 d)	Week 8 Day 57 (±2 d)	Week 9 Day 64 (±2 d)	NA
Informed consent	X									
Demographics	X									
Fitzpatrick skin type	X									
Medical history ^d	X	X ^e								
Assess/confirm eligibility	X	X								
Serum/urine pregnancy test (WOCBP) ^f	X	X ^g					X		X	X
Brief physical examination ^h	X	X					X		X	X
Vital signs ⁱ	X	X	X	X			X		X	X
ECG ^j		X					X		X	X
Blood sample for clinical laboratory tests ^k	X	X ^l					X		X	X ^m
Urinalysis	X	X ⁿ					X		X	X ^m
PK sample ^o							X		X	
Subject randomization		X								
Photograph representative of disease area ^p		X		X			X		X	
Adverse events	X	X	X	X	X	X	X	X	X	X
Concomitant medication	X	X	X	X	X	X	X	X	X	X
Investigator Assessed										
vIGA-AD TM score ^q	X	X	X	X			X		X	X
%BSA affected ^q	X	X	X	X			X		X	X
EASI ^q	X	X	X	X			X		X	X
LTS ^r		X	X	X			X		X	X
Completed by Subject or Caregiver										

Procedures and Assessment	Screening	Baseline	Double-Blind Vehicle-Controlled Treatment Phase						FU ^a	ET ^b
	V1	V2	V3	V4	P/C ^c	V5	P/C ^c	V6	V7	NA
	Day -30 to Day -1	Day 1	Week 1 Day 8 (±2 d)	Week 2 Day 15 (±2 d)	Week 3 Day 22 (±2 d)	Week 4 Day 29 (±2 d)	Week 6 Day 43 (±2 d)	Week 8 Day 57 (±2 d)	Week 9 Day 64 (±2 d)	NA
PP-NRS (pre-dose) ^s		X	X	X		X		X	X	X
LTS ^r		X	X	X		X		X		X
Dispense (D)/collect (C) diary ^t		D	C/D	C/D		C/D		C		C
Review subject diaries for treatment compliance			X	X		X		X		X
Dispense (D)/Collect (C) study drug		D	C/D	C/D		C/D		C		C
Review instructions for study drug application ^u		X	X	X	X	X	X			
Study drug application under supervision ^v		X	X	X		X				
Enrollment (optional) in OL-LTE study								X		

a. The Follow-up Visit will be performed for any subject who completes Visit 6/Week 8 but fails to qualify for participation in the OL-LTE study or qualifies to participate in the OL-LTE study but elects not to enroll in that study. A follow-up visit is not required for a subject who early terminates.

b. Subjects who withdraw from the study before Visit 6 (Week 8) will complete an Early Termination Visit. A follow-up visit is not required for a subject who early terminates.

c. Phone calls to assess AEs and concomitant medications, to review study drug application procedures, and to confirm subject's continued participation in the study. Subjects should be reminded to complete the diary and bring it with them to the next clinic visit.

d. Medical history will include year of AD diagnosis, CV family history, allergic conditions, and risk factors (including height, weight, medical conditions) and family history of liver disease. As part of the subject's medical history, all systemic (oral and injectable) medications used by the subject for treatment of AD prior to 30 days before the Screening visit will be collected.

e. Review medical history at Baseline and record any changes.

f. Serum pregnancy test to be performed at the Screening visit only and urine pregnancy test to be performed at subsequent clinic visits when pregnancy testing is performed.

g. Urine pregnancy test to be performed before randomization.

h. Physical examination will include height and weight (BMI will be calculated in the CRF) at the Screening visit; a brief physical examination will be performed at other visits.

i. Vital signs will include blood pressure, pulse rate, and body temperature and should be measured after the subject is seated for at least 5 minutes. Vital signs will be measured before blood collection for clinical laboratory assessments and PK analysis (where applicable).

j. ECGs will be collected in a subset of subjects and will be collected prior to study drug administration in clinic. Informed consent/assent will be required.

k. Includes serum chemistry and liver chemistry tests, and hematology.

l. Blood sample collection for clinical laboratory tests is not required at the Baseline Visit if it has been ≤14 days since samples were collected at Screening and the results of those clinical laboratory tests were not clinically significant.

m. If needed, laboratory testing at the Follow-up visit for ongoing AEs or abnormal laboratory values.

n. Urine sample collection for urinalysis is not required at the Baseline Visit if it has been \leq 14 days since samples were collected at Screening and the results of those analyses were not clinically significant.

o. Blood sample for PK will be collected in a subset of subjects. Sample to be collected prior to study drug application in clinic. Informed consent/assent will be required.

p. Photography will be performed in a subgroup of subjects at selected study sites. Informed consent/assent and photographic release will be required.

q. The vIGA-ADTM assessment should be performed before the %BSA and EASI assessments. The subject's scalp should be excluded from the vIGA-ADTM, %BSA, and EASI calculations.

r. The LTS assessment consists of an Investigator-assessed and a subject (or caregiver)-assessed component. Both the Investigator-assessed LTS and subject (or caregiver)-assessed LTS should be completed within 2 hours post-dose at Weeks 1, 2 and 4. At Week 8 and the ET visit, when study drug is not applied, the LTS should be completed when other assessments are completed. If the subject (or caregiver) is applying study drug to "sensitive areas" (face, neck, skin folds, axilla, inframammary, anal crux, and/or genitalia), the Investigator will also complete a separate LTS assessment for each sensitive area where study drug is being applied.

s. Subjects (or Caregivers) should perform the PP-NRS assessment daily and record the results in their diary. When subjects dose in the clinic on study visit days, subjects will not complete the diary at home; application time and PP-NRS will be recorded in the clinic.

t. Subjects will be instructed on when and how to complete diaries.

u. Subjects will be instructed to apply study drug QD at the approximate same time each day, based on subject preference.

v. At clinic visits, study drug will be applied after safety and efficacy assessments have been conducted (except for LTS at Weeks 1, 2 and 4).

AD = atopic dermatitis; AE = adverse event (s); BMI = body mass index; %BSA = percent of total BSA; C = collect; [REDACTED] ; CRF = case report form; CV = cardiovascular; d = day(s); D = dispense; [REDACTED] ; [REDACTED] ; ET = early termination; EASI = Eczema Area and Severity Index; ECG = electrocardiogram; FU = follow-up; [REDACTED] ; LTS = Local Tolerability Scale; NA = not applicable; OL-LTE = Open-Label, Long-Term Extension Study; P/C = phone contact; PK = pharmacokinetic; [REDACTED] ; PP-NRS = Peak Pruritus-Numeric Rating Scale; QD = once daily; V = Visit; WOCBP = women of child-bearing potential; vIGA-ADTM = Validated Investigator Global Assessment in Atopic Dermatitis.

1 Introduction

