5.2 Randomization/Treatment Assignment

For the double-blind, vehicle-controlled phase of the study, subjects will be randomized at a ratio of 2:1 to receive tapinarof cream, 1% or vehicle cream as follows:

Randomization in Double-Blind, Vehicle-Controlled Phase	
Regimen	Number of Subjects
Tapinarof cream, 1% QD for 8 weeks	Approximately 267 Subjects
Vehicle cream QD for 8 weeks	Approximately 133 Subjects

QD = once daily

Randomization will be stratified by Baseline vIGA-AD™ score so that subjects with severe AD (vIGA-AD™ score of 4) will be limited to approximately 10% each of the total randomized population, and the majority of the enrolled subjects (approximately 90%) will have a vIGA-AD™ score of 3, signifying moderate disease.

Randomization will also be stratified by age so that a minimum of approximately 15% of subjects will be enrolled into each of the following age groups: 2-6 years, 7-11 years, 12-17 years, 18 years and above. Adults 18 years and above will comprise a maximum of 20% of enrolled subjects.

The randomization lists will be generated using a validated system, which involves a pseudo-random number generator so that the resulting treatment will be both reproducible and non-predictable. Access to the codes will be controlled and documented.

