10.4.2.2 Secondary and Exploratory Efficacy Endpoint Analyses

The secondary efficacy endpoints are as follows:

- Proportion of subjects with $\geq 75\%$ improvement in EASI from Baseline at Week 8
- Mean change in %BSA affected from Baseline at Week 8
- Proportion of subjects with $\geq 90\%$ improvement in EASI from Baseline at Week 8

- Proportion of subjects ≥ 12 years old with a Baseline PP-NRS score ≥ 4 who achieve ≥ 4 -point reduction in the PP-NRS from Baseline at Week 8

Exploratory efficacy endpoints are as follows:

The same methods as discussed for the primary analysis of the primary endpoint will be used to analyze all dichotomized secondary endpoints. The secondary efficacy endpoints will be tested sequentially in the order listed. Testing will stop if non-significance (2-sided $p \geq 0.05$) is observed.

Post-baseline weekly PP-NRS scores will be an average of 7 daily post-baseline PP-NRS scores prior to and including the values assessed on the visit date.

Other efficacy endpoints will be analyzed using CMH test for proportions, and analysis of covariance (ANCOVA) model for continuous variables. CMH tests will be stratified by Baseline vIGA-AD™ score and age group, and ANCOVA models will include vIGA-AD™ score and age group as categorical covariates and Baseline as a continuous covariate.

All endpoints will be summarized descriptively as follows: continuous data will include the mean, SD, minimum, maximum, median, and number of observations; descriptive summary statistics for categorical data will include frequency counts and percentages.

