10.3 Adjustments for Covariates

The model for the primary, secondary, and exploratory efficacy analyses will include adjustments for the following covariates:

Continuous secondary and exploratory efficacy endpoints (excluding Functional Outcomes and Quality of Life Endpoint) analyzed using ANCOVA models will include baseline vIGA-ADTM score and age group as a categorical covariate and the baseline value as a continuous covariate (see Section 11.2 and Section 11.3).

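### The visible ANCOVA for functional, quality-of-life and PP-NRS change scores omits the randomization strata, a small and conservative loss, and the text conflicts on the PP-NRS model

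*Protocol*

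**What the plan says.** **Randomization.** Protocol 5.2 stratifies by baseline vIGA-AD and by four age groups: "subjects with severe AD (vIGA-AD™ score of 4) will be limited to approximately 10% each of the total randomized population" and "Randomization will also be stratified by age so that a minimum of approximately 15% of subjects will be enrolled into each" of the age groups, with adults capped at 20%.

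**Models that use the strata.**
- The primary CMH test (Protocol 10.4.2.1, SAP 11.1).
- The dichotomized secondary endpoints, which follow the primary method, and the other proportions: "CMH tests will be stratified by Baseline vIGA-AD™ score and age group" (Protocol 10.4.2.2).
- Other continuous efficacy endpoints: "ANCOVA models will include vIGA-AD™ score and age group as categorical covariates and Baseline as a continuous covariate" (Protocol 10.4.2.2).
- The %BSA ANCOVA, through an eight-level age-by-vIGA-AD cohort (SAP 11.2).

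**The model that does not.** The protocol synopsis, under Functional Outcomes and Quality of Life Analysis, names a redacted set of scales and then PP-NRS: "Peak Pruritus-NRS scores will be analyzed using an ANCOVA model with treatment as a main effect, and baseline as a covariate". Neither stratum appears.

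**The exemption.** SAP 10.3 sets the general rule with a carve-out: "Continuous secondary and exploratory efficacy endpoints (excluding Functional Outcomes and Quality of Life Endpoint) analyzed using ANCOVA models will include baseline" vIGA-AD, age group and the baseline value. SAP 14 reports no changes to the protocol-specified analyses.

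**The status of PP-NRS.** Protocol 3.1 lists it among the efficacy assessments, beside vIGA-AD, %BSA and EASI.

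**The concern.** Stratified randomization balances the arms on vIGA-AD and age group. If those factors predict the change score beyond its own baseline value, the treatment estimate already benefits from the balance. A model without them leaves their variance in the residual. The reported standard error is then larger than the estimate's true variability, so intervals over-cover and tests reject less often than their nominal level.

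Age could matter for PP-NRS. Under Protocol 6.2.2.3 the caregiver scores below 12 years and the subject scores from 12 years. That switch falls on the boundary between the 7-11 and 12-17 strata, so an age-group term would absorb it.

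At stake is precision for the objective on symptom severity and daily impact. There is also a question of specification: two analysts reading the visible text could fit different models to PP-NRS change, and the choice should be settled before unblinding.

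**Working it through.** **1. The plan's own figure.** The only power statement concerns the primary endpoint: 45% against 25%, 267 against 133 subjects, two-sided 0.05, Fisher exact, 97.2% (Protocol 10.2, SAP 5). Exact enumeration of the two-sided Fisher test gives 97.6%. A continuity-corrected sample-size formula at 97.2% power and 2:1 returns 133 vehicle subjects. The figure reproduces and does not bear on this point. The documents give no SD, effect size or power for the change scores.

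**2. Inputs.** From the documents: N = 400, allocation 2:1, four age groups each at least about 15%, adults at most 20%, about 10% severe, two-sided 0.05. Assumed: R², the share of variance left after the baseline score that the strata explain. The working range is 2% to 10%, with 20% as a stress value.

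**3. Formulas, under stratified randomization.**
- Ratio of reported SE without strata to SE with strata: k = 1/√(1 − R²).
- True size of the nominal 5% test without strata: 2 × [1 − Φ(1.96 × k)].
- Power without strata when the adjusted model has 80%: Φ(1.96 + 0.8416 − 1.96 × k).

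Example at R² = 10%: k = 1/√0.90 = 1.054. The effective critical value is 1.96 × 1.054 = 2.066, size is 2 × [1 − Φ(2.066)] = 0.039, and power is Φ(2.8016 − 2.066) = 0.769.

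**4. Results.** The simulation used N = 400, blocks of 6 within 8 strata, ages 27/27/27/19%, 10% severe, baseline correlation 0.5 and 6,000 runs per row. Block size, age mix and correlation are assumptions.

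| Assumed R² | SE ratio, formula | SE ratio, simulated | Size, formula | Size, simulated | Power, formula |
|---|---|---|---|---|---|
| 0 | 1.000 | 1.000 | 0.050 | 0.050 | 80% |
| 2% | 1.010 | 1.010 | 0.048 | 0.046 | 79.4% |
| 5% | 1.026 | 1.026 | 0.044 | 0.047 | 78.5% |
| 10% | 1.054 | 1.054 | 0.039 | 0.037 | 76.9% |
| 20% | 1.118 | 1.118 | 0.028 | 0.030 | 72.9% |

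Monte Carlo error on a simulated size is about 1.96 × √(0.05 × 0.95/6000) = ±0.006. With the strata in the model, simulated size was 0.048 to 0.052 throughout.

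**5. With the planned dropout.** SAP 10.4 does not impute missing functional or quality-of-life data, and the plan assumes 15% and 30% loss. That leaves 267 × 0.85 ≈ 227 and 133 × 0.70 ≈ 93, about 320 in all. At R² = 10% the simulated SE ratio is 1.05 and size is 0.045. Loss after randomization undoes part of the balance, which moves the size back towards 5%.

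**6. PP-NRS change, passages side by side.** The synopsis places it in the functional family with treatment and baseline only. Protocol 3.1 calls it an efficacy assessment, and Protocol 10.4.2.2 then gives it vIGA-AD, age group and baseline. SAP 10.3 allows either result, depending on the family to which PP-NRS is taken to belong.

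**The case against.** **The governing sections are not visible.** Protocol 10.4.4 is redacted, and the relevant SAP text in Section 11 cannot be read. SAP 10.3 says which rule these endpoints escape, not which covariates they receive. This is fair as a caution, and a reason for the exemption may stand in the hidden text. But the synopsis and SAP 10.3 point the same way in unredacted words, so the visible model and exemption can be reviewed as they stand.

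**Age-specific scales.** Protocol 6.2.2 and the title of Appendix 5 show that patient-reported assessments differ by age. For a scale used in one age band, a four-level age term is redundant and N = 400 is too many. This stands, and the fix allows for it. It would not explain dropping vIGA-AD, nor dropping age for PP-NRS, which is collected from age 2 upward.

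**PP-NRS is not a settled omission.** Correct. A reader might infer from the synopsis that the final PP-NRS change model lacks the strata, but Protocol 3.1 and 10.4.2.2 support the opposite reading. The finding there is a conflict.

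**The effect is conditional and small.** Also correct. If the strata add 1% or less beyond baseline, there is no practical effect. At R² of 2% to 5% the simulated sizes cannot be told apart from 0.05.

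**No decision depends on it.** The objective is descriptive, and SAP 10.7 keeps these change scores out of the fixed testing sequence. This limits the weight of the point without removing the inconsistency.

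**Conclusion.** The point holds as a minor one. The visible model for functional, quality-of-life and PP-NRS change scores leaves out the stratification factors used in the other visible inferential efficacy models. The exemption in SAP 10.3 carries no visible reason, and the PP-NRS change model is stated inconsistently.

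If the strata explain 2% to 10% of the remaining variance, the standard error is about 1% to 5% too wide and the nominal 5% test runs at about 4.8% to 3.9% with complete data. With the planned loss it is about 4.5% at the upper end of that range. These figures rest on an assumed R², on N = 400 (too large for any scale limited by age), and on the simulation settings above.

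Two stronger readings are not supported:
- A reader might infer that the tests are invalid or the estimates biased. The error is conservative only: intervals over-cover, false positives do not rise, and randomization keeps the estimate unbiased.
- A reader might infer that the PP-NRS secondary endpoint is compromised. That endpoint is the responder rate for a reduction of at least 4 points in subjects aged 12 and over, analyzed by the stratified primary method (Protocol 10.4.2.2, SAP 11.2). The rater switch at 12 does not arise there, and no primary or sequentially tested secondary conclusion changes.

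**What to change.** 1. Delete the exemption for functional and quality-of-life endpoints in SAP 10.3.
2. Amend the protocol synopsis, with the matching text in Protocol 10.4.4 and the SAP, so that the ANCOVA for these change scores contains treatment, the baseline score, baseline vIGA-AD and age group. Use only the age levels that apply to each scale. Changing the SAP alone would leave the synopsis as it is and make the statement in SAP 14 untrue.
3. State this one model for PP-NRS change in both documents.

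The cost is a few words in each document, settled before unblinding. Both factors are already collected for randomization and used in the other models, so no data, visits or subjects are added. With complete data the adjusted test held its nominal size in every simulated setting (0.048 to 0.052), and the simulated standard error was essentially unchanged when the strata explained nothing (ratio 1.000).
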